
Eligibility and recruitment. Two recruitment methods will be used. Veterans with chronic musculoskeletal pain who self-report functional impairment will be referred by their PACT, in response to a recruitment flyer posted in primary care, or by contacting the PI or study staff directly after hearing of the study by word of

mouth or other sources, including ClinicalTrials.gov. This

[figure not shown]

Figure 1: Recruitment and procedures.

approach will be supplemented by a case-finding procedure in which study staff review electronic medical record data to identify potential patients. Initial eligibility criteria will target those Veterans who are age ≥18 years to 79 years, conversant in English, have an established history of VA primary care utilization (i.e., at least one primary care visit in the past year), and a diagnosis of musculoskeletal pain of ≥3 months. This pain definition is consistent with the consensus definition of chronic pain from the International Association for the Study of Pain^{46,47} and is well-matched to the study goal of addressing chronic pain proactively. Veterans meeting these initial eligibility criteria will be sent a study invitation letter signed by their primary care provider. Following the letter, Veterans will be contacted by phone for additional screening in which they will first be asked to verify the presence of current musculoskeletal pain for ≥ 3 months. The PEG^{48,49}, a validated 3-item pain measure^{48,49}, will also be administered. Veterans must score ≥4 on the PEG pain intensity item and ≥4 on either of the PEG pain interference items to be included. Veterans will be excluded at this stage if they self-report current engagement

in behavioral health services that may include cognitive or behavioral interventions (i.e., behavioral medicine intervention, specialty mental health services, or standard PC-MHI). Veterans receiving only psychopharmacological intervention from a mental health provider will not be excluded. Veterans will also be excluded if they report uncontrolled medical conditions, scheduled/planned surgeries, or other interventions likely to impact pain/functional outcome ratings. Potential participants will not be excluded based on past/current/future use of chiropractic care or physical therapy.

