In situations where the referring primary care provider and Veteran would rather directly connect to the study staff in-person, a letter will not be sent. Rather, and when feasible, study staff will be notified of the Veteran's preference to be screened at time of referral (or shortly thereafter) by study staff.

Veterans who meet telephone screening criteria will be scheduled for a face-to-face baseline interview. Following informed consent and HIPPA authorization procedures, assessment measures will be administered. Veterans will be screened for active suicidal ideation based on responses to the Patient Health Questionnaire9 (PHQ-9)⁵⁰. Veterans will be excluded from participation if they score >0 on PHQ-9 item 9 and also endorse imminent suicide risk (i.e., in response to additional questions that will differentiate suicide risk versus

nonsuicidal morbid ideation). Veterans will be excluded on the basis of probable substance use problems (e.g., alcohol, cannabis, opioids, benzodiazepines) if they score positive (≥8) on the Alcohol Use Disorders Identification Test⁵¹ (AUDIT) or score positive (≥3) on the Drug Abuse Screening Test⁵² (DAST-10). Veterans will also be excluded if their baseline administration of the BPI is <4 on the pain intensity items and <4 on pain interference items. Participants will also be excluded if they are unwilling to have their treatment sessions audio recorded.

Electronic medical record review will be used to identify if the patient is currently prescribed relevant pain or psychiatric medications. If relevant medications are prescribed, study staff will supplement this review by asking the patient to verbally verify if the medication(s) identified in the chart are 1) currently in use by the patient, 2) what the current schedule/frequency of use of that medication, and 3) if there have been changes in the past 2 months. Veterans will be excluded if relevant medications have been modified in the past 2 months. Use of over-the-counter (OTC) analgesic medications/topicals will not be considered an exclusion criterion, even if these agents are recorded in the patient's medical record by a VA provider. Similarly, routine or PRN use of prescribed anti-inflammatory medications (i.e., acetaminophen, aspirin, ibuprofen, naproxen) or topical agents will not be considered an exclusion criterion.

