Patients will be excluded if chart review indicates either of the following: 1) unstable psychiatric status (e.g., active psychosis, current mania) or 2) major or minor neurocognitive disorder (e.g., dementia). Patients will also be excluded if chart review reveals uncontrolled medical conditions, scheduled/planned surgeries, and medical or other interventions likely to impact pain/functional ratings. Potential participants will not be excluded based on past/current/future use of chiropractic care or physical therapy.

Procedures. As shown in Figure 1, upon completing baseline measures, eligible participants will be randomly assigned to (1) Brief CBT-CP plus TAU or (2) TAU only. Assignment to Brief CBT-CP will be stratified based on degree of pain interference as measured by West Haven-Yale Multidimensional Pain Inventory – Interference (WHYMPI-I)⁵³. Participants will be classified as average interference and below (WHYMPI-I score ≤ 4.4) or as above average interference (WHYMPI-I score >4.4)^{28,53}. All participants will complete a telephone-based follow-up with the study coordinator, who will be blinded to participants' condition, at 8 weeks (post-test) and at 12 weeks (follow-up) from randomization for re-administration of study measures. Participants will be compensated \$40 for the initial assessment and \$30 for each of two follow ups (total \$100 for Aim 1). We will replace dropouts who do not meet minimum treatment completion requirements of attending ≥ 4 sessions. Attending, at minimum, sessions one through four will provide patients with essential education and core CBT self-management skills. Although some dropout is planned, we predict that we will replace only a small number of participants (~3-4) prior to our final 12-week follow-up assessment. This prediction is informed by [name] (Co-I) current clinical trial (IIR I01HX000909) of a brief behavioral intervention for depression conducted at the Buffalo VAMC primary care clinics which used similar methodology. At 90% completion, this study has evidenced only 11.3% participant drop out at 12-week follow-up.

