during follow-up assessment calls. To assess the suitability of our measures of patient outcome measures, we will examine item response rates, including the number of missed responses and multiple responses, and time required for completion. We will also document any questions or comments raised by the participant during measure administration. To assess fidelity of service delivery, the study interventionist will complete an adherence checklist after each session. Checklists map on to each of the six sessions of Brief CBT-CP and will be designed to capture key content and procedures. All intervention sessions will be audio recorded with the participant's permission. The PI will randomly select 25% of the audio recordings for review by [name] (study Co-I) using an adapted version of the CBT-CP Rating Scale⁵⁵. To examine the precise nature of participants' service utilization during the trial, we will conduct a chart review at 12-week follow-up. Chart review will assess participants' engagement in primary medical care (i.e., PACT encounters), PC-MHI encounters, and other VA services to assist with assessing feasibility of TAU only as a control condition and will assess any changes in pain or psychotropic medication initiated since baseline assessment. Aim 1 Measures of patient outcomes. Patient outcome measures will be assessed at baseline, post treatment (eight weeks), and follow-up (12 weeks). Administration of all study measures will take about one hour at each time point.

- West Haven-Yale Multidimensional Pain Inventory Interference (WHYMPI-I). The WHYMPI-I is a validated 9-item subscale that evaluates pain-related interference in daily activities and social and occupational functioning⁵³. It is among the core assessments included in the full-length CBT for Chronic Pain³² and is the primary patient outcome for this trial.
- Brief Pain Inventory Short Form (BPI-SF): The BPI-SF is a psychometrically validated 9-item measure that assesses pain level (current and average), pain related functional impairment, and activity interference. The BPI-SF asks participants to indicate the extent of their pain as well as any interference with various activities and other aspects of life (i.e., mood, relationships) using a scale ranging from 0 (no pain/interference) to 10 (worst pain/complete interference). This measure is included in order to further assess pain outcomes in response to Brief CBT-CP.

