Primary feasibility outcomes: Feasibility outcomes will be assessed using descriptive statistics. We will calculate the percentage of patients who met preliminary eligibility criteria (identified via chart review) who were reached for telephone screening, including refusal rate. We will calculate the proportion of patients who screen eligible and either 1) refuse. 2) consent to and complete the baseline interview, but are not randomized for failure to meet study criteria, or 3) consent to and complete the baseline interview and are randomized. Refusal and recruitment rates will 1) indicate if our initial inclusion criteria and our screening methods are in need of modification, and 2) assist with estimating the total number of patients who will need to be screened to account for failures or refusals. Retention will be evaluated by computing the rates of withdrawal from the trial, or percentage of those randomized who do not complete all study procedures. Low retention rates will suggest that patients are facing barriers to completing the treatment (e.g., Brief CBT-CP may need to be abbreviated further). The feasibility and acceptability of patient assessment measures will be assessed through item response rates. This information will assist with assessing participant burden and will indicate which measures are highest in utility (i.e., easily completed by participants and show change over the study period). Assessment of treatment fidelity indicators will include analysis of session checklists completed by the interventionist, which will indicate the percentage of Brief CBT-CP content delivered (i.e., dosage). Scores on the checklists will be compared to the adherence ratings from the modified CBT-CP Rating Scale⁵⁵ for a subsample of recorded sessions to determine if these data sources show appropriate convergence.

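### Does the baseline BPI check need to be tightened because it excludes only Veterans below 4 on both pain intensity and interference?

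*Combined protocol and SAP*

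**What the plan says.** The combined protocol and SAP applies two pain thresholds in turn, both under Eligibility and recruitment.

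- **Telephone screen (PEG).** "Veterans must score ≥4 on the PEG pain intensity item and ≥4 on either of the PEG pain interference items to be included".
- **Sequence.** "Veterans who meet telephone screening criteria will be scheduled for a face-to-face baseline interview".
- **Baseline check (BPI).** Veterans are "excluded if their baseline administration of the BPI is <4 on the pain intensity items and <4 on pain interference items".

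Under Procedures, "upon completing baseline measures, eligible participants will be randomly assigned to (1) Brief CBT-CP plus TAU or (2) TAU only". Under Aim 1 Measures of patient outcomes, the BPI-SF is described as a "psychometrically validated 9-item measure that assesses pain level (current and average), pain related functional impairment, and activity interference", with responses on a 0–10 scale. No section says which items make up the intensity or interference score used for eligibility, or whether a mean, any item or every item must be below 4.

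Primary feasibility outcomes counts Veterans who "consent to and complete the baseline interview, but are not randomized for failure to meet study criteria", so a failed BPI check feeds a reported rate.

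**The concern.** The telephone rule requires both domains to be elevated. Its logical complement is exclusion when *either* domain is low, yet the baseline rule joins the two conditions with 'and'. It uses the same cut-off of 4 on the same two domains and gives no reason for being looser. A Veteran with intensity 3 and interference 7, or the reverse, falls short of the telephone standard at baseline and still proceeds.

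Two things would be at stake. First, the baseline screen-failure rate helps the team judge the criteria and plan screening numbers for a larger trial, and it depends on how the rule is read and scored. Second, participants with low interference at entry might have little room to improve on WHYMPI-I, the primary patient outcome.

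**Working it through.** **1. Logic of the two rules.** Let I be the intensity score and F the interference score, each a whole number from 0 to 10, giving 11 × 11 = 121 combinations.

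- Excluded as worded (I < 4 and F < 4): 4 × 4 = 16.
- Excluded under the complement of the telephone rule (I < 4 or F < 4): 121 − 7 × 7 = 72.
- Status differs: 72 − 16 = 56.

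The wording is therefore looser than the telephone rule. These are counts of score combinations, not proportions of patients.

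**2. Which reading the text supports.** The same paragraph joins AUDIT and DAST-10 with 'or', where either one excludes. For PHQ-9 item 9 and imminent suicide risk, where both are needed, it uses 'and also'. That contrast favours the literal reading of the BPI sentence.

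**3. Whether the literal rule contradicts the screen.** It does not, because both checks must be passed. Those who reach baseline have already scored at least 4 on PEG intensity and on a PEG interference item. The BPI check then removes only those no longer elevated on either domain. Having been selected for high scores on one noisy measure, some people will score lower on a second through ordinary fluctuation. A lenient second check avoids turning them away after consent for that reason.

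**4. Size.** The documents give no BPI distribution, so every input here is assumed:

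- intensity mean 5 or 6, SD 1.7; interference mean 5 or 6, SD 2.2;
- correlation between domains 0.5 or 0.7;
- PEG-to-BPI correlation within a domain 0.6 to 0.9;
- domain share of item variance 0.7.

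That makes 32 scenarios of 400,000 draws each, keeping only those who pass the PEG. Ranges run across scenarios.

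| Interference scored as | Fails literal rule | Fails 'either domain' rule | Low on exactly one domain, among admitted |
|---|---|---|---|
| either of two items | 0.3–4.0% | 4.5–18.4% | 4.1–15.8% (about 1–5 of 30) |
| mean of items | 0.8–7.4% | 10.9–28.3% | 9.6–23.9% (about 3–7 of 30) |

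Completed baselines needed to randomise 30, on this criterion alone, are 30 / (1 − failure rate). With either-of-two scoring:

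- literal rule: 30 / 0.997 = 30.1 to 30 / 0.960 = 31.3;
- stricter rule: 30 / 0.955 = 31.4 to 30 / 0.816 = 36.8.

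The stricter rule therefore needs about 1–6 more interviews, each taking about an hour and $40. If both means are instead 6.5–7, with PEG-to-BPI correlation 0.7–0.9, the share low on exactly one domain falls to about 2–5% with either-of-two scoring (30 × 0.02 = 0.6 to 30 × 0.05 = 1.5 people) and 4–8% with mean scoring.

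**5. Scoring.** Take illustrative intensity items {2, 4} and interference items {2, 3, 5}. The domain means are 3.0 and 3.33, so the literal rule excludes on means. It also excludes if any item below 4 counts. It does not exclude if every item must be below 4. The missing definition can therefore change an individual's eligibility.

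**6. Effect on the analysis.** Eligibility is decided before assignment, so neither reading can favour an arm. Procedures stratifies on WHYMPI-I at 4.4 and expects a stratum at or below average interference. Exploratory analysis of patient outcomes adjusts for the baseline score by ANCOVA.

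**The case for a change.** The best case for a change is that feasibility is the purpose of this pilot, so an eligibility rule open to more than one reading weakens a primary output. The chart-review exclusions under Eligibility and recruitment do list "uncontrolled medical conditions, scheduled/planned surgeries, and medical or other interventions likely to impact pain/functional ratings" with 'and', although any one of these plainly suffices. Staff could carry that usage over to the BPI sentence. Whatever the conjunction means, the score itself is undefined. The PEG rule names its items, while the BPI-SF is said only to be a measure that "assesses pain level (current and average), pain related functional impairment, and activity interference". Stratification and ANCOVA balance and adjust for low interference, but they would not create room to improve where there is none.

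The scoring gap stands, as does the lack of a stated reason for the looser check. The rest carries less weight. The chart-review sentence is a list of nouns, and the neighbouring score-based criteria are closer evidence of how the authors use 'and' and 'or'. The feasibility rates are descriptive, with no progression threshold that a few percentage points could cross. The BPI is recorded at baseline, so the failure rate can be tabulated under either reading and any scoring afterwards. No figure in the documents links a BPI interference score below 4 to a floor on WHYMPI-I, and the analyses concerned are labelled exploratory.

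**Conclusion.** No change is called for. The baseline rule is looser than the telephone rule, but the documents do not show it to be wrong. Followed as written, it gives a valid randomised comparison and interpretable descriptive rates. Moving to an 'either domain' exclusion would be a trade-off rather than a correction: about 1–6 more post-consent screen failures, against removing about 1–5 of 30 participants who are low on one domain and had already met the two-domain standard by telephone. Those figures rest wholly on assumed score distributions and either-of-two scoring. They rise with mean scoring and fall if the recruited Veterans are more impaired than assumed.

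What remains is missing detail: which BPI items are compared with 4, how they are combined, and confirmation that 'and' is meant. Staff can settle this in the working procedures and state the scoring used when results are reported. It does not affect the sample size of 30 or the trial's conclusions.

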To assist with recruitment throughout the study, study staff will conduct reminder phone calls for all appointments 48-24 hours ahead of time reminding participants of the time and location of the meeting. Reminder letters containing date, location, and purpose of study contact will be sent prior to baseline, 8-week, and 12-week follow-up. Reminder letters will be sent for therapist appointments on an as-needed basis (e.g., when requested by participant). At least two phone attempts will be made (and one letter sent) to reach participants who do not show for scheduled contacts.

Participants will be provided with a behavioral health resource sheet at the end of their participation (or as needed during the trial) should they wish to access additional VA or community services.

Measures of feasibility. Our study measures focus on indicators of feasibility of trial processes^{43,54}. To assess feasibility of participant screening, recruitment, and retention, study staff will track the number of potential

participants identified by primary care team referral as well as our case finding procedure. We will document the number of potentially eligible participants who are sent study invitation letters, the number completing/refusing a screening call, and number who agree/refuse to be scheduled for baseline interview. We will track the number of participants who are randomized to compute actual enrollment rate (vs. planned enrollment), including time to reach full sample accrual. Within the Brief CBT-CP plus TAU condition, we will monitor treatment retention by assessing number of sessions attended, as well as the number of patients completing a full course of treatment. We will attempt to ascertain the reason for drop-out, when applicable,

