- Working Alliance Inventory Short Form Revised (WAI-SR): The WAI-SR is a 12-item self-report measure that asks participants about their perceptions of their therapist (i.e., my therapist and I respect each other) and the therapeutic services they receive (i.e., what I am doing in therapy gives me new ways of looking at my problem). Participants indicate on a scale from 1 (seldom) to 5 (always) how well each statement describes their own experiences in therapy. This instrument is included in the current protocol in order to examine potential differences in treatment outcomes as a result of the participants' rapport with their study therapist.
- **Demographics Form:** This form requests standard information on patient demographic background, including the following: age, gender, race, living arrangements, marital status, education, and occupation.

Aim 1 Study conditions.

Brief CBT-CP plus TAU: Brief CBT-CP is a manualized protocol that includes six, 30-minute sessions over the course of 6 weeks. Brief CBT-CP session outlines and patient handouts are included in the appendix. Session one focuses on foundational pain education and the development of treatment goals. Session two emphasizes balanced engagement in physical activity and pleasurable events. Session three emphasizes skills training for easily implemented relaxation techniques. Sessions four and five focus on recognizing and modifying unhelpful thoughts that negatively impact pain. Session six focuses on relapse prevention and independent implementation of CBT-CP skills following treatment. Brief CBT-CP will be delivered by a masters-level interventionist either at the Buffalo VA Medical Center or by telephone depending on the preference of the participant. The interventionist will be trained by Drs. [name] (Co-I) and [name] (PI) in how to apply the protocol. Training will include at least 20 hours of didactic explanations of the principles of each intervention, role play and feedback exercises, discussion of case examples, and skill rehearsal. Audio recordings of sessions will be reviewed by [name]. If the interventionist has deviated significantly from the protocol based on CBT-CP Rating Scale⁵⁵ scores, or related measures, s/he will be provided with corrective feedback and assigned training cases until deficiencies are corrected.

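### The blinded coordinator's 8-week call is also where drop-out reasons are asked, which can reveal the arm before the 12-week WHYMPI-I is collected

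*Combined protocol and SAP*

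**What the plan says.** All references are to the combined protocol and SAP.

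- **Procedures.** Study measures are repeated at 8 and 12 weeks from randomization in a "telephone-based follow-up with the study coordinator, who will be blinded" to condition. Participants who attend fewer than four sessions are to be replaced. On their number the plan says "we predict that we will replace only a small number of participants (~3-4"), citing a related trial at the same clinics: "this study has evidenced only 11.3% participant drop out at 12-week follow-up".
- **Measures of feasibility.** "Within the Brief CBT-CP plus TAU condition, we will monitor treatment retention by assessing number of sessions attended" and the number completing treatment. The next sentence reads "We will attempt to ascertain the reason for drop-out, when applicable", and it places this "during follow-up assessment calls".
- **Aim 1 Study conditions.** Brief CBT-CP is six sessions over six weeks. The TAU-only arm gets no behavioral intervention from the clinic's PC-MHI provider.
- **Aim 1 Measures of patient outcomes.** The WHYMPI-I is the primary patient outcome. The same list includes the WAI-SR, a self-report scale meant to examine "rapport with their study therapist".
- **Exploratory analysis of patient outcomes.** A preliminary effect size on the WHYMPI-I is produced at post-treatment and at follow-up.

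**The concern.** Two stated procedures work against each other. One keeps the person collecting outcomes unaware of the arm. The other puts on the follow-up calls a question that, for anyone who left therapy, is answered by talking about therapy. The text names no other caller, sets no order of questions, and does not say which of the two calls carries the drop-out question.

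Two things are at stake. The smaller is interviewer influence on telephone-collected WHYMPI-I scores, which feed the preliminary effect size at both time points. The larger concerns the pilot's purpose. Under the design overview, the study is meant to show whether its processes are workable for later effectiveness trials, and blinded outcome assessment by telephone is one of those processes. A later trial could inherit a call script that breaks its own blinding.

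**Working it through.** The first four steps compare the text; the last two give the size.

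**1. Who makes the calls.** Procedures assigns the 8- and 12-week calls to the coordinator. Measures of feasibility refers to follow-up assessment calls without naming a caller. No other follow-up assessment calls are described, so the plain reading is that they are the same calls.

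**2. What kind of drop-out.** The sentence just before the drop-out question is limited to the Brief CBT-CP arm and concerns session attendance. Procedures also ties drop-out to sessions attended. The natural reading is drop-out from treatment, which only one arm can have. The question is not expressly limited to that arm, however, and Primary feasibility outcomes defines retention over everyone randomized. Withdrawal from the trial itself could occur in either arm and need not reveal it.

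**3. Timing.** Six weekly sessions normally end before week 8, so most treatment drop-out has already happened by the first call. If the reason is asked at week 8, the arm can be known 12 − 8 = 4 weeks before the 12-week WHYMPI-I. It can also be known before the 8-week WHYMPI-I if that is not completed first. Asking last at week 8 protects only the 8-week score.

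**4. Knowing when the question applies.** To ask only where applicable, the coordinator must either be told who stopped attending, which gives the arm, or put the question to everyone and learn it from the answer.

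**5. How many participants.** The plan predicts about 3 to 4 replacements.
- Cited rate applied to all 30: 0.113 × 30 = 3.4, which matches the prediction.
- Cited rate applied to one arm of 15: 0.113 × 15 = 1.7, about 2.
- The cited rate is participant drop-out at 12 weeks, whereas the replacement rule concerns fewer than four sessions, so the two are not the same quantity.
- Share of the Brief CBT-CP arm: 3/15 = 20% to 4/15 = 27%. If replacements are added to those replaced: 3/18 = 17% to 4/19 = 21%. With 2 participants: 2/15 = 13%.

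**6. Possible effect on the WHYMPI-I effect size.** The documents give no figure for assessor influence. As an assumption only, take a shift b of 0.1 to 0.3 SD per exposed participant and none in TAU. The shift in the arm mean is (m/15) × b:

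| Exposed, m | b = 0.1 | b = 0.3 |
|---|---|---|
| 0 | 0 | 0 |
| 2 | 0.013 | 0.040 |
| 3 | 0.020 | 0.060 |
| 4 | 0.027 | 0.080 |

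For comparison, take the planned non-central t interval at an observed d of 0 with 15 per arm. The non-centrality limits are ±1.96, so the limits for d are ±1.96 × √(1/15 + 1/15) = ±1.96 × 0.365 = ±0.72. The largest shift in the table is about one ninth of that half-width (0.72/0.08 = 9).

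**The case against.** The strongest case against is that the conflict is conditional and its numerical effect trivial. The plan does not say that the coordinator personally asks about drop-out. Question order is normally settled in a call script, not a protocol. Participants know their arm and rate themselves, so blinding the caller removes only the interviewer's share of bias. The primary outcomes are descriptive feasibility rates. Those who drop out may not be reached at all, and if the data of replaced participants are not analysed, the effect on the effect size is nil; the plan does not say whether they are.

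Most of this stands, and it limits the point to a modest one. It does not remove the conflict. The plan itself claims a blinded caller and itself places the drop-out question on follow-up assessment calls, so following it as written can unblind. That goes beyond a missing detail.

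There is also a fair objection to the remedy. Holding drop-out reasons until week 12 loses people reached only at week 8 and lengthens recall, and retention is a primary feasibility matter. This is why the fix offers a second route.

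A reader might infer three stronger things that the documents do not support:

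- **That the coordinator also gives the WAI-SR, unblinding most of the treated arm.** The scale sits in a list assessed at baseline, 8 and 12 weeks, but it cannot be given at baseline, before there is a therapist. It is described as self-report, no administrator is named, and Figure 1 is not available here. This is a query, not a finding, and no bias figure for the whole arm should be drawn from it.
- **That any unblinding would go unrecorded.** Measures of feasibility has staff note participants' questions and remarks while measures are given, which could capture a disclosure. What the plan lacks is a dedicated count.
- **That the statement about a blinded coordinator should be withdrawn.** The number likely to be exposed is small, and the conflict can be removed by reordering the calls.

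**Conclusion.** The point holds in limited form. As written, the 8-week call can reveal the arm to the person who collects the 12-week WHYMPI-I, and possibly before the 8-week one.

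The expected exposure is about 3 to 4 Brief CBT-CP participants on the plan's own prediction. It is nearer 2 if the cited 11.3% is applied to one arm, and none if those participants are not reached. Under the assumed 0.1 to 0.3 SD per exposed participant, the effect size moves by 0 to 0.08 SD, well inside the pilot's sampling error. No conclusion about efficacy turns on this. It matters because blinded telephone assessment is a process the pilot should be able to report on.

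The conclusion rests on two readings: that the follow-up assessment calls are the coordinator's, and that drop-out here mainly means leaving treatment. Both are the natural readings, but neither is stated outright, so confidence is medium.

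**What to change.** 1. On each call, complete the WHYMPI-I and all other outcome measures before anything else is asked.
2. Ask drop-out reasons only after all outcome measures at the 12-week call, or have an existing team member other than the coordinator ask them. The second route keeps those who can be reached only around week 8. Either way, the coordinator should not be told beforehand who stopped attending.
3. At the end of each call, have the coordinator record whether the arm became known and how. Report the count as a feasibility result.
4. Query to the sponsor: confirm that the blinded coordinator does not give the WAI-SR. If the coordinator does, have it self-completed or given by someone else, in the Brief CBT-CP arm only.

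**Cost.** Script wording and one line per call: 30 × 2 = 60 calls, or up to 34 × 2 = 68 if four replacements are enrolled and those replaced are still followed. The documents do not describe staffing, so whether another team member is free is an assumption; deferring the question to week 12 avoids needing one. The downside of deferral is that fewer drop-out reasons may be obtained.
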